Participants will participate across 14 weeks. Those in Intervention first (Group A) will participate in three caregiver meetings held every two weeks across six weeks. This will be followed by data collection check-ins over 8 weeks. The second group (Group B) will begin with 8 weeks of data collection check-ins, followed by three caregiver meetings over 6 weeks. Each meeting will be scheduled every two weeks and last 60 minutes. Survey check-ins will be repeated six times

Protocol: EnACT RCT

Version: 7/20/2025

and will include completion of a survey via phone or internet. Two weeks after the final intervention meeting, participants will be invited to meet together to discuss thoughts about the caregiver training activities.

Frequency and duration of intervention. EnACT will be offered three times to each person. It will occur every two weeks for a total of three 60-minute sessions. Each participant will be invited to complete one take-home written exercise after session 1 and session 2, which will involve journaling about topics related to the session.

Study assessments for caregivers will include (total time = 95 minutes):

Baseline survey: 20 minutes

Time 2 survey: 15 minutes

Time 3 survey: 15 minutes

Time 4 survey: 15 minutes

Time 5 survey: 15 minutes

Time 6 survey: 15 minutes

Additional time commitments will include:

Study Eligibility Interview: 15 minutes

Final debrief focus group: 60-90 minutes

Reimbursement

Caregivers will receive \$25.00 for each caregiver meeting that they attend, \$10 for the completion of three surveys gathered outside of meetings, and \$50 to attend the final focus group meeting. It is possible to receive \$155.00 total in compensation. Payment will be distributed at the end of the study either through direct deposit or check. You will only be paid for each visit or survey that you complete. If you discontinue early from the study, you will receive a partial amount based on how many meetings and surveys you complete.

Assessment Schedule

Survey data will be gathered at six time points no less than two weeks apart over the course of control, intervention, and follow up.

Focus group data will be gathered during the debrief meeting two weeks after intervention meetings are complete.

Feasibility and Acceptability data will be gathered throughout. Satisfaction surveys will be gathered at the end of each intervention session as part of the session.

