Baseline Assessment (T1): Demographics, Imagined Interactions, Capacity to Adapt, Caregiver Capacity to Appraise Demands, Perceived Stress, Caregiver Well-being

Survey Assessment (Week 2 (T2), Week 5 (T3), Week 8 (T4), Week 11 (T5), Week 14 (T6): Imagined Interactions, Capacity to Adapt, Caregiver Capacity to Appraise Demands, Perceived Stress, Caregiver Well-being

Measures

Feasibility: number screened and enrolled, retention rates, levels of engagement, intervention delivery, assessment-protocol duration, and completion rates

Acceptability: satisfaction with intervention, audio/video documentation of intervention meetings, post-intervention focus groups

Focus Groups: questions on suggestions for improvement, preference compared to other programs they've experienced, barriers to or benefits of use.

Demographics: age, education, gender identity/sexual orientation, race/ethnicity, employment, salary, caregiving experience, frequency of theatre attendance, care-recipient relationship, caregiver support, time as caregiver, type of caregiver, sex and age of care partner, participation in caregiver training or support, type of caregiver training/support, frequency of caregiver training/support, activity/hobbies and frequency of participation.

Imagined Interactions: *Survey of Imagined Interactions* (7-point Likert scale questions) measures outcomes of imagining interactions, including four subscales: *Specificity* (5 items), *Discrepancy* (7 items), *Proactivity* (3 items)

Capacity to Adapt: *Resilience Scale* (7-point Likert scale questions) measures one's ability to adapt, specific to constructs of meaning, self-confidence, perseverance, serenity, and loneliness (25 items)

Caregiver Capacity to Appraise Demands: *Revised Caregiving Appraisal Scale* (RCAS; 5-point Likert scale questions) asks ADRD caregivers to assess the following five subscales: *Burden* (9 items), *Satisfaction* (6 items), *Mastery* (4 items), *Demand* (3 items), *Impact* (3 items)

Perceived Stress: *Perceived Stress Scale* (5-point Likert scale questions) measures self-reported stress (10 items)

Caregiver Well-being: *Modified Caregiver Burden Inventory* (CBI; 5-point Likert scale questions) 24 items comprising five subscales: *Time*, *Physical*, *Social*, *Emotional*, *Developmental*. *Positive Aspects of Caregiving Scale* (PAC; 5-point Likert scale questions) measures the perceptions of the benefits of caregiving (9 items.)

Data Collection and Management

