- inability to cope
- hospitalization due to emotional factors
- suicide attempts
- death
- any type of reported or suspected abuse (participant as victim or abuser)

Some events may be classified as **Unanticipated Problems (UP)**, defined as any incident, experience, or outcome that meets all of the following criteria: 1) unexpected, in terms of nature, severity, or frequency, given (a) the research procedures that are described in the protocol-related documents, such as the IRB-approved research protocol and informed consent document; and (b) the characteristics of the study population; 2) related or possibly related to participation in the research procedures; 3) suggests that the research places participants or

others at a greater risk of harm (including physical, psychological, economic, or social harm) than was previously known or recognized.

The vast majority of adverse events occurring in human subjects are not unanticipated problems, but a small proportion of adverse events are unanticipated problems. Unanticipated problems include other incidents, experiences, and outcomes that are not adverse events.

Collection: Study staff will monitor any potential adverse event or unanticipated problem through every phone call with participants and study staff, during live sessions with study participants, or as expressed by participants on each questionnaire or other data collection instrument. This type of general monitoring of participant safety and well-being will be conducted on an ongoing and continual basis, during each interaction between study participant and study staff.

If there is evidence that an adverse event may have potentially occurred during the study period (i.e., from consent through the end of the study), study staff will immediately (within 24 hours) complete an adverse event reporting form on paper, where they describe the event and classify it based on the following grading and attribution criteria:

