Protection Against Risks: All possible precautions will be taken to protect the safety, privacy, and confidentiality of all persons contacted to be in the project and for those who consent to participate.

Project staff will be trained to continually monitor for negative emotional responses either during their contact with the participants or as indicated on any of their submitted questionnaires. If a participant is discovered to be experiencing distress or an adverse event, the PI will address the specific issues, answer questions, and if necessary, assist the participant in formally withdrawing from the study if desired. If needed, participants will be referred (or to preserve confidentiality, will be provided information so that they can refer themselves) to sources of professional help within the community. In the event that the study staff have identified a serious adverse event (SAE), the participant will be administratively withdrawn from the study; their participation in the study will be automatically and immediately discontinued.

To protect participant privacy and confidentiality,

- All participants will be identified in study files and monitoring reports by identification numbers, not names or other identifying characteristics.
- All study-related information and data will be password-protected with access limited to CITI-certified research staff only. Study data will be de-identified.
- All communication (verbal or written) among project staff regarding any participant will use ID numbers only. Email communications will contain “PHI” in the subject line, which automatically encrypts the message until retrieved on a secure server.
- Unattended workstations will be locked and only able to be unlocked with a password.
- Once all of the study data are gathered, entered and cleaned for errors, the personally identifying information (name, phone and address) will be deleted and any hard copies destroyed.

Interim Analysis

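### Adverse events are collected without a standard question, while scheduled contact in weeks 2-8 differs by group; one identical survey item would close the gap cheaply

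*Combined protocol and SAP*

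**What the plan says.** All references are to the combined protocol and SAP.

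- **AE collection** (Adverse Event and Serious Adverse Event Collection and Reporting, Collection paragraph). "Study staff will monitor any potential adverse event or unanticipated problem through every phone call with participants and study staff, during live sessions". The same sentence adds a questionnaire route: "or as expressed by participants on each questionnaire or other data collection instrument". Monitoring takes place "during each interaction between study participant and study staff" and the period runs "from consent through the end of the study".
- **Distress** (Protection Against Risks). Staff also watch for negative emotional responses in their contacts or "as indicated on any of their submitted questionnaires".
- **Sessions and debriefs** (Study Design). Group A meets at weeks 2, 4 and 6 with a debrief at week 8. Group B meets at weeks 8, 10 and 12 with a debrief at week 14. Time Commitment says: "The second group (Group B) will begin with 8 weeks of data collection check-ins".
- **Surveys** (Assessment Schedule). The schedule is common to both groups, with a baseline and then "Survey Assessment (Week 2 (T2), Week 5 (T3), Week 8 (T4), Week 11 (T5), Week 14 (T6): Imagined Interactions, Capacity to Adapt" and the remaining scales, including perceived stress and caregiver well-being.
- **Survey mode.** Time Commitment says the check-ins "will include completion of a survey via phone or internet". Data Collection and Management lists paper, online and phone in one paragraph, and in another says questionnaires are delivered in person.
- **Use of AE data.** AEs are classified one by one, discussed by the internal committee, and summarised for the funder and the IRB. The Analysis section plans no AE comparison between groups.

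**The concern.** Collection depends on what staff notice or what participants volunteer. No question is put to every participant at fixed times, and there is no rule for who reads a returned questionnaire, how soon, or what score or comment counts as an event. Under such a system the number of recorded events depends on the number of contacts as well as on the number of events, and contact differs by group in the period when Group B is untreated.

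Two things are at stake. The first is participant safety. The 24-hour AE form and the expedited reports start only once staff know of an event. The AE section's own examples include hospitalization for emotional reasons, suicide attempts and abuse, and the Measures section describes no instrument that asks about these. The second is interpretation. AE summaries go to the committee and the funder, and the pilot is meant to inform a full-scale trial. A reader who sets Group A's weeks 2-8 count beside Group B's could take a difference in contact for a difference in safety, or dismiss a real difference as contact. There is also a possible knock-on effect: the protocol administratively withdraws a participant once a serious event is identified, so unequal detection could produce unequal missing data at week 8.

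**Working it through.** The document gives no safety figure to reproduce. The check counts scheduled contacts and then illustrates what they could do.

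**Step 1: count contacts.** Inputs: surveys at weeks 0, 2, 5, 8, 11 and 14 in both groups (Assessment Schedule); sessions at weeks 2, 4, 6 (A) and 8, 10, 12 (B); debrief at week 8 (A) and 14 (B) (Study Design).

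| Window | Group A | Group B |
|---|---|---|
| Week 2 up to, not including, week 8 | 2 surveys + 3 sessions = 5 | 2 surveys = 2 |
| Weeks 2-8 inclusive | 3 surveys + 3 sessions + 1 debrief = 7 | 3 surveys + 1 session = 4 (3 without the session) |
| Weeks 8-14 inclusive | 3 surveys + 1 debrief = 4 | 3 surveys + 3 sessions + 1 debrief = 7 |
| Whole study | 6 + 3 + 1 = 10 | 6 + 3 + 1 = 10 |

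Scheduled live time in weeks 2-8 for Group A is 3 x 60 + (60 to 90) = 240 to 270 minutes. For Group B before its week 8 session it is 0 minutes, but only if every survey is done online; a phone or in-person survey is staff contact.

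**Step 2: check whether the common surveys close the gap.** The Perceived Stress Scale (10 items) and the burden inventory are in every survey, so the mildest listed AE domain (stress, fatigue, sadness) is at least partly measured at the same weeks in both groups. The remaining scales cover imagined interactions, resilience, caregiving appraisal and positive aspects of caregiving. None is described as asking about hospitalization, suicide attempt or abuse. The forms themselves are not in the document, so this rests on the descriptions in Measures.

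**Step 3: illustrate the possible size.** Assume each contact after an event detects it independently with probability p, the same for every type of contact. Detection over k contacts is 1 - (1 - p)^k. The document gives no value for p; 0.1, 0.2 and 0.4 are assumptions.

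Take an event just after week 2. Group A has k = 5 later contacts by week 8 (sessions at 4 and 6, surveys at 5 and 8, debrief at 8). Group B has k = 3 (surveys at 5 and 8, session at 8), or k = 2 if the week 8 session is left out.

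| p | A, k = 5 | B, k = 3 | Ratio | B, k = 2 | Ratio |
|---|---|---|---|---|---|
| 0.1 | 0.410 | 0.271 | 1.51 | 0.190 | 2.16 |
| 0.2 | 0.672 | 0.488 | 1.38 | 0.360 | 1.87 |
| 0.4 | 0.922 | 0.784 | 1.18 | 0.640 | 1.44 |

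The ratio is what equal true rates would look like. The k = 3 column is the fairer one, because Group A's week 8 debrief is counted too. For an event just after week 6, Group A has 2 contacts (survey, debrief) and Group B has 2 (survey, session), so the ratio is 1.0. A lower p for online surveys than for live contacts would widen the ratios; a higher p for surveys done by phone or in person would narrow them.

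**Step 4: apply the fix.** If by-group counts use only events elicited by an identical survey item, the opportunities in weeks 2-8 inclusive are 3 against 3.

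**The case against.** The strongest case against is that no safety comparison exists to be distorted. The independent-samples tests are for baseline equivalency, the regression models are for the main and secondary outcomes, and the stated goal is feasibility and acceptability in a minimal-risk pilot of 30. This stands: a reader might infer that a randomised safety comparison is biased, or that the intervention will look less safe than waiting, and the document supports neither.

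A reader might also infer that events are found only when staff happen to be in contact, or that waitlist distress goes unseen. The questionnaire route in the same sentence contradicts the first, and the stress and burden scales in every survey contradict the second. What is missing is a standard question and a rule for reviewing what comes back.

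It can further be said that unequal contact is inherent in a waitlist design, that contacts total 10 in each group, and that surveys may bring staff contact. The equal totals do not remove the problem, because from week 8 Group B is itself receiving the intervention; the reversed imbalance in weeks 8-14 does not repair the untreated comparison. The survey-mode point stands in part: the passages on internet completion and in-person delivery disagree, and the gap is widest only for someone who answers entirely online.

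**Conclusion.** The point holds as a gap in ascertainment and a low-cost improvement. AE collection has no standard question; scheduled contact in weeks 2-8 is 7 against 4 (5 against 2 before week 8); and a waitlist caregiver completing surveys online has no described prompt to report a hospitalization, suicide attempt or abuse.

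For interpretation, any by-group reading of AE counts in that window is open to unequal ascertainment. The document does not allow its size to be estimated. Under the illustration, counting Group B's week 8 session, equal true rates would appear as a ratio of about 1.2 to 1.5 for an event just after week 2 and 1.0 for one just after week 6. Leaving that session out raises the first range to about 1.4 to 2.2, which is the less favourable count. All of these rest on assumed values of p applied equally to every contact.

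**What to change.** - Add one identical short AE item, with a checklist of the event types the AE section already lists, to the week 2, 5, 8, 11 and 14 surveys in both groups. Set a REDCap alert to the principal investigator for online completion, and state who reviews responses and by when.
- Report AEs descriptively by group and period (weeks 2-8 and 8-14), with survey-elicited events shown separately from those noticed at sessions or debriefs. All events still follow the existing reporting rules.
- Reconcile Time Commitment with Data Collection and Management on how surveys are completed.

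The cost is an estimated one minute per survey: 5 x 1 = 5 minutes on the planned 95 minutes of assessment, with no extra visits or staff. The recorded AE count will rise because events are asked about, and the report should say so. The item cannot help when a survey is not returned.
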